### **Durable Response Rate (DRR)**

Durable response rate is defined as the percent of subjects with a CR or PR per modified irRC-RECIST with a DOR  $\geq$  6 months. One month will be calculated based on 365.25 days per year.

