- ^x Radiographic tumor imaging: During treatment, radiographic tumor imaging will be performed independent of treatment cycle at week 10 (\pm 1 week) and then every 9 weeks (\pm 1 week) until confirmed progressive disease (PD) per modified immune-related response criteria (irRC) simulating RECIST version 1.1 (irRC-RECIST) ([Appendix D](#)). Radiographic imaging is required at the safety follow up visit if the subject ended treatment prior to documentation of confirmed PD per modified irRC-RECIST and has not had radiographic tumor imaging performed within 9 weeks (\pm 1 week) of the visit. Every effort should be made to complete radiographic assessments during the long-term follow-up every 12 weeks (+ 1 week) until documented confirmed PD per modified irRC-RECIST, start of new anticancer treatment, death, or end of study, whichever occurs first, for subjects discontinuing study treatment for any reason other than confirmed PD. Response (complete response [CR], or partial response [PR]) or disease progression to be confirmed by second consecutive radiographic assessments no less than 4 weeks from the date of the first documented response or disease progression. Note: Confirmation of disease progression is required only in the absence of rapid clinical deterioration (ie, rapid decline in performance status) or symptomatic disease requiring rapid initiation of alternative systemic anti-cancer therapy.
- ^y To be performed if required by site for assessment of the intrahepatic lesion injection location. **As of Protocol Amendment 6 (dated 26 October 2021), intrahepatic injections of talimogene laherparepvec and liver biopsies are no longer performed in this study.**
- ^z If no progression is seen after a total of 12 cycles, a total of 35 cycles of talimogene laherparepvec, at maximum tolerated dose if known or otherwise previously received dose, every 21 (\pm 3 days) may be administered, or the subject may proceed to alternative therapies depending on investigator discretion. Dosing with talimogene laherparepvec beyond 12 cycles may be done if in the opinion of the investigator, the subject is deriving clinical benefit.

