### **Duration of Response (DOR)**

Duration of response is defined as the time from the date of an initial response that is subsequently confirmed to the earlier of PD (see definition of BOR per modified irRC-RECIST) or death. Subjects who have not ended their response at the time of analysis will be censored at the last evaluable tumor assessment before start of the first subsequent anticancer therapy.

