### **Objective Response Rate (ORR)**

The incidence rate of either a confirmed CR or PR per Modified irRC-RECIST. Subjects who do not achieve confirmed CR or PR by the start date of subsequent anticancer therapy or the data cutoff date, whichever occurs earlier, are regarded as non-responders.

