## **7.2 Primary Analysis**

**One clinical study report (CSR) will be written based on the results of the primary analyses across Part 1 and Part 2.**

**The primary analysis for each combination cohort from Part 2 will occur independently when all subjects in each tumor type arm have a minimum potential follow-up of  $\geq 29$  weeks. The primary analysis for part 1 will occur after all subjects have a minimum potential follow-up of  $\geq 29$  weeks. The database will be cleaned, and a locked database will be used in the analysis.**

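### The durable response rate in the primary report is biased low, because 6 months of response cannot be observed in subjects with less than about 37 weeks of follow-up and the analysis is triggered at 29

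*SAP*

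**What the plan says.** **Endpoint.** SAP section 5 (Durable Response Rate): "Durable response rate is defined as the percent of subjects with a CR or PR per modified irRC-RECIST with a DOR" of at least 6 months, and "One month will be calculated based on 365.25 days per year". SAP section 5 (Duration of Response) measures DOR as the "time from the date of an initial response that is subsequently confirmed to the earlier of PD" or death. It adds: "Subjects who have not ended their response at the time of analysis will be censored at the last evaluable tumor assessment" preceding any new anticancer therapy.

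**Estimator.** SAP Table 9-2 gives DRR, like ORR and DCR, as a rate with a 95% CI in the Full Analysis Set. The sensitivity column reads N/A. Kaplan-Meier estimates of DOR are planned, with 1-, 2- and 3-year landmarks as examples. There is no follow-up or evaluability rule specific to DRR.

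**Timing.** SAP 7.2 and Protocol 10.3.3 set the trigger: "primary analysis for each combination cohort from Part 2 will occur independently when all subjects in each tumor type arm have a minimum potential follow-up" (29 weeks or more). Part 1 has the same 29-week trigger and also reports DRR.

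**Scans.** Protocol Table 13, footnote x: "radiographic tumor imaging will be performed independent of treatment cycle at week 10" and then every 9 weeks, each with a window of one week either way. Confirmation takes at least 28 days. For ORR, "Subjects who do not achieve confirmed CR or PR by the start date of subsequent anticancer therapy" or by the data cutoff, whichever is earlier, are non-responders.

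**Later data.** SAP 7.3 plans a final report with updated results. Protocol 7.2.3.2 continues Part 2 follow-up to about 24 months after the last enrolment in the tumor cohort.

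**The concern.** The 29-week trigger is set for ORR, where a responder needs one qualifying scan and a confirmation. DRR needs a further 26 weeks after the first qualifying scan, yet it is reported from the same data cut. A subject enrolled late may be in a deep, ongoing response and still be unable to meet the definition at that cut. If such subjects stay in the denominator and count as failures, the reported proportion mixes true non-durability with short follow-up. The binomial interval around it does not reflect that. Durability is one of the main reasons to read a single-arm response rate as promising, so an artificially low DRR could mislead readers of the primary report.

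**Working it through.** **1. The plan's own figures.** The documents give no expected DRR. The two-stage ORR design does reproduce: continue with at least 2 of 10, reject with at least 6 of 21. Exact binomial calculation gives one-sided alpha 0.0133, power 0.8839, and stopping probabilities 0.7361 (H0) and 0.0464 (H1). The stated values are 1.3%, 88.4%, 73.6% and 4.6%.

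**2. Threshold.** 6 × 365.25 / 12 = 182.6 days = 26.1 weeks.

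**3. Longest DOR visible with 29 weeks of follow-up.**
- Week-10 response to cutoff: 29 − 10 = 19 weeks = 133 days.
- Censored at the week-28 scan: 28 − 10 = 18 weeks = 126 days.
- Most favourable reading (week 10 taken as 9 elapsed weeks, scan one week early): 29 − 8 = 21 weeks = 147 days.

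All are below 182.6 days. Working backwards, 203 − 182.6 = 20.4, so the response would have to be documented by day 20, long before the first scan.

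**4. Follow-up needed.**

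| First response | Calendar minimum (+26.1 weeks) | First scheduled scan that shows it |
|---|---|---|
| Week 10 | 36.1 | Week 37 |
| Week 19 | 45.1 | Week 46 |
| Week 28 | 54.1 | Week 55 |

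**5. Size of the bias.** Assumptions, none of them from data: ORR 40%; first responses 50/30/20% at weeks 10/19/28; 75% of responders durable, so true DRR = 0.40 × 0.75 = 30%; n subjects accrued uniformly over A weeks; cutoff 29 weeks after the last actual enrolment. The expected share of subjects enrolled at least g weeks before the last one is approximately (n − 1)/n − g/A. The three rows above need g = 37 − 29 = 8, 46 − 29 = 17 and 55 − 29 = 26.

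For n = 21, A = 40: 20/21 = 0.952, so the shares are 0.752, 0.527 and 0.302. Expected DRR = 0.30 × (0.5 × 0.752 + 0.3 × 0.527 + 0.2 × 0.302) = 0.178.

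| n | A (weeks) | Share, week 10 | Share, week 19 | Share, week 28 | Expected DRR (true 30%) |
|---|---|---|---|---|---|
| 21 | 40 | 0.752 | 0.527 | 0.302 | 17.8% |
| 21 | 104 | 0.876 | 0.789 | 0.702 | 24.5% |
| 10 | 40 | 0.700 | 0.475 | 0.250 | 16.3% |
| 10 | 104 | 0.823 | 0.737 | 0.650 | 22.9% |

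Simulation agrees with these values. The 104 weeks is roughly the time from Amendment 3 (21 October 2019), which set the current Part 2 non-HCC tumor types, to Amendment 6 (26 October 2021), which records that enrolment has stopped. It is not a reported accrual time for any arm.

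A second set of assumptions gives the same picture: true DRR 24%, first responses 60/30/10%, cutoff 29 weeks after the end of the accrual window. Expected DRR is then 12.5%, 18.2% and 21.1% for accrual over 26, 52 and 104 weeks.

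**6. Effect on ORR.** A first response at week 28 can be confirmed at week 32 at the earliest (week 30 on the most favourable reading), after week 29. With a repeat scan at week 32, g = 3. For n = 21, A = 40 the share is 0.952 − 0.075 = 0.877, and expected ORR = 0.40 × (0.80 + 0.20 × 0.877) = 39.0%. Across the four rows the loss is 0.6 to 1.4 points. If confirmation waits for the week-37 scan (g = 8), it is 1.0 to 2.4 points.

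**The case against.** **DRR is secondary, and the final analysis already repairs it.** Protocol 10.4 limits formal analysis to the Part 2 primary endpoints, and no threshold or decision hangs on DRR. Follow-up to about 24 months exceeds the 55 weeks needed. This stands: only the primary report is affected.

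**Twenty-nine weeks is a minimum.** Earlier-enrolled subjects can qualify, and with slow accrual most do. This stands too. A reader might infer that DRR would come out at a third or less of its true value. That needs a small arm filled within a few months, and the documents give no accrual by arm. Also, if the single primary report used one common cut for all arms, arms that closed earlier would have longer follow-up. SAP 7.2, however, times each arm independently.

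**The SAP never says that a censored response is non-durable, or that the primary DRR will be presented as mature.** Correct. Counting it as non-durable is the literal reading of a proportion over the full set. If it is not what is intended, the rule is missing.

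**Kaplan-Meier DOR is in the same report.** It handles censoring properly, and the listed landmarks are only examples. But 6 months is not among them, so the report need not contain the figure that would put DRR right.

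**The ORR test.** A reader might infer that the primary test is compromised and the cut must move. The documents do not support that. The expected loss is small and makes rejection harder, not easier. One unconfirmed responder could turn 6 of 21 into 5, but a list of such cases makes that visible.

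**Conclusion.** The timing conflict is certain. On every reading of the scan schedule, a subject with 29 weeks of follow-up cannot have an observed 6-month response. Followed literally, the plan gives a primary-report DRR that is biased low, with an interval that ignores the incomplete follow-up. Under the assumptions stated, a true 30% would be expected to appear as about 16–18% with accrual over 40 weeks and about 23–24% over 104 weeks. These figures depend on the assumed response timing, durability and accrual. The shortfall vanishes only if no subject with short follow-up has an ongoing response that would become durable. The point concerns a descriptive secondary endpoint in one report. It does not show that the final DRR is wrong, and it is not a reason to change the ORR analysis.

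**What to change.** Amend SAP section 5 (Durable Response Rate) and Table 9-2:

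- **Primary report, preferred.** Estimate DRR as ORR × the Kaplan-Meier probability of DOR of at least 6 months, with the interval method named. Add a 6-month DOR landmark and the number of responders censored before 6 months. Apply this to Part 1 as well.
- **Primary report, alternative.** Restrict DRR to subjects with at least 55 weeks of potential follow-up. This is simpler but gives wider intervals: 53 Part 2 subjects over six arms average 53/6 = 8.8 per arm before any restriction.
- **Final report.** Name the full-set DRR at the final analysis as the definitive estimate.
- **ORR.** Keep the 29-week cut and list separately any first response near week 28 that is unconfirmed at the cutoff.

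The cost is SAP wording and a little programming. Moving the ORR cut would mean amending the protocol (sections 3.5.2, 10.2 and 10.3.3) for a small gain, so it is not asked for.

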### **Disease Control Rate (DCR also called the Clinical benefit response rate)**

Disease control rate is the proportion of subjects that have a best overall response of confirmed CR/ PR or SD.

### **Objective Response Rate (ORR)**

The incidence rate of either a confirmed CR or PR per Modified irRC-RECIST. Subjects who do not achieve confirmed CR or PR by the start date of subsequent anticancer therapy or the data cutoff date, whichever occurs earlier, are regarded as non-responders.

### **Baseline Lesion**

Baseline lesion is defined as the lesions identified on or before study day 1 with a positive tumor length. If a baseline lesion has a positive tumor length reported at more than one visit, then the length from the most recent visit will be selected as the baseline length.

### **New Lesion**

New lesion is defined as the lesions that first appear after study day 1 with a positive tumor length. "Baseline" (ie, initial) tumor length of a new lesion will be obtained from the earliest date with a positive tumor length. Lesions that split from other lesions will not be considered as new lesions.

#### **Lesion complete response (L-CR)**

Lesion complete response (L-CR) is a response at the lesion level in injected vs uninjected lesions and applies only to target lesions and new measurable lesions. For injected and uninjected lesions, L-CR is defined as complete disappearance of a non-nodal or reduction in short axis to <10 mm for pathological lymph node with confirmation by a repeat consecutive assessment no less than 4 weeks (28 days) after first documented.

#### **Lesion partial response (L-PR)**

Lesion partial response (L-PR) is a response at the lesion level in injected vs uninjected lesions and applies only to target lesions and new measurable lesions and is defined as  $\geq 30\%$  decrease in lesion length relative to baseline with confirmation by a repeat consecutive assessment no less than 4 weeks (28 days) from the date first documented.

#### **Lesion objective response rate (L-ORR)**

Lesion objective response rate (L-ORR) is a response rate at the lesion level in injected vs uninjected lesions and is defined as the incidence among a set of lesions analyzed of L-CR or L-PR.

Response at the lesion-level will be censored at the earliest **after the start of the first subsequent anticancer therapy**, or on or after the event of merging with another lesion, or complete or partial removal/reduction of any target lesion which contained cancer on pathology evaluation or pathology results were unknown. If a lesion splits, the sum of the length of the split lesions will be added together prior to analysis.

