## Best overall response (BOR) per Modified irRC-RECIST

Best overall response (BOR) of complete response (CR), partial response (PR), stable disease (SD), progressive disease (PD) or un-evaluable (UE) will be derived based on investigator assessment using modified irRC-RECIST as defined in protocol Appendix D.

Overall visit response assessments occurring after the start of the first subsequent anticancer therapy **will not be included. With the exception of a PD observation, the overall visit response** occurring on or after complete or partial removal/reduction of any target lesion which contained cancer on pathology evaluation or pathology results were unknown, will not be included. Consecutive confirmation of CR, PR, and PD is required where the second overall response must be at least 28 days from the first, the only exception being when the investigator reports that an initial PD cannot be confirmed due to rapid clinical deterioration. The following will be considered a confirmed PR: CR followed by PR or PR followed by CR.

BOR is defined as the best visit response in the following order: CR, PR, SD, PD, or UE (see [Table 1](#)). BOR is defined as SD if the best overall visit response is an unconfirmed CR or PR, and UE if it is either SD earlier than 77 days after first dose date or an unconfirmed PD when confirmation of PD is required (ie, initial PD without rapid clinical deterioration).

Table 1. Matrix of Determining BOR per Modified irRC-RECIST

Visit Overall Response Sequence	Examples	Best Overall Response	Confirmation specifications
*, CR, CR,*	PR, CR, CR CR, CR, PD	CR	The confirmatory CR must be at least 4 weeks (28 days) later; a subsequent CR within 28 days will not be valid for

			confirmation and will be ignored; the CR will also not be confirmed if there is a subsequent PR/SD/PD at any time prior to the next CR.
* , PR, PR, *  * , PR, CR/PR, non-CR, *  * ,CR, PR,*	PR, PR, PD PR, CR, PD  CR, PR, PD	PR	Criteria for BOR=CR not met. The confirmatory PR/CR must be no less than 4 weeks (28 days) later; a subsequent PR/CR within 28 days will not be valid for confirmation and will be ignored; the PR will also not be confirmed if there is a subsequent SD/PD at any time prior to the next PR/CR.
* , SD, *  * ,CR, non-PR/CR, *  * ,PR, non-PR/CR, *	CR PD, CR PR PD, PR, SD SD PD,SD,PD	SD	Criteria for BOR=CR or PR not met. SD must be $\geq 77$ days from the date of first dose; however, this is not required for an unconfirmed CR/PR.

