#### **Maximum Tumor Burden Decrease**

Tumor burden is defined as the sum of the diameters (longest for non-nodal lesions, short axis for nodal lesions) for all target lesions and up to 10 (maximum 5 per organ) new measurable lesions. Tumor burden ratio is defined as the ratio of the tumor burden at each assessment divided by the baseline tumor burden. The Maximum tumor burden decrease is defined as smallest tumor burden ratio among all assessments -1.

The maximum tumor burden decrease at the subject-level will be censored **at the earliest after the start of the first subsequent anticancer therapy, or on or after the event of** complete or partial removal/reduction of any target lesion which contained cancer on pathology evaluation or pathology results were unknown.

The maximum tumor burden decrease at the lesion-level will be censored at the earliest after the start of **the first subsequent anticancer therapy**, or on or after the event of merging with another lesion, or complete or partial removal/reduction of any target lesion which contained cancer on pathology evaluation or pathology results were unknown. If a lesion splits, the sum of the length of the split lesions will be added together prior to analysis.

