## **6.11 Lesion Analysis Sets**

The Injected Lesion Analysis Set includes any target lesion and new measurable lesion that was ever injected and the uninjected lesion analysis set includes any target lesion and new measurable lesion that was never injected among subjects in Full Analysis Set. The Injected Lesion Evaluable and Uninjected Lesion Evaluable analysis sets will include the corresponding subset of target lesions and new measurable lesions with at least one post-baseline measurement prior to a censoring event, ie, non-study anticancer therapy, merged with another lesion, or resection (except if it is partial or complete resection and pathology indicates absence of malignant cells). If a lesion splits, the sum of the length of the split lesions will be added together prior to analysis.

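### The SAP's surgical cut-offs for lesion response and maximum tumor burden decrease name only target lesions, although both measures also include new measurable lesions

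*SAP*

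**What the plan says.** **Which lesions count.** In SAP Section 5, lesion complete response (L-CR) "applies only to target lesions and new measurable lesions", and lesion partial response has the same scope. Tumor burden, which underlies maximum tumor burden decrease, is summed "for all target lesions and up to 10 (maximum 5 per organ) new measurable lesions". For a new lesion, the reference "tumor length of a new lesion will be obtained from the earliest date with a positive tumor length", so a new lesion can show shrinkage of up to 100% from its own first measurement.

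**Where follow-up is cut off after surgery.** For lesion objective response rate (L-ORR), Section 5 lists the start of subsequent anticancer therapy, merging with another lesion, "or complete or partial removal/reduction of any target lesion which contained cancer on pathology evaluation or pathology results were unknown". Under *Maximum Tumor Burden Decrease*, the subject-level and lesion-level paragraphs both use the same condition: "complete or partial removal/reduction of any target lesion which contained cancer on pathology evaluation or pathology results were unknown".

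**A different rule in Section 6.11.** The evaluable lesion sets contain "target lesions and new measurable lesions with at least one post-baseline measurement prior to a censoring event". The censoring events listed there are non-study anticancer therapy, merging, "or resection (except if it is partial or complete resection and pathology indicates absence of malignant cells"). Nothing limits that list to target lesions.

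**Protocol.** Section 6.6 allows lesions to be resected on study and excludes responses due to surgery from ORR and BOR only. Appendix D makes the response unevaluable, except for progression, after resection of a lesion with tumor or unknown pathology. It still allows the later measurements to be used for tumor burden. SAP Table 9-2 plans waterfall plots at subject and lesion level.

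**The concern.** The surgical cut-off exists so that shrinkage produced by the surgeon is not credited to the study treatment. In Section 5 it covers fewer lesions than the measures it protects. Read literally, removing a new measurable lesion that contained cancer stops nothing: later assessments stay in the subject-level waterfall and in the lesion-level response.

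The situation is foreseeable. Resection is permitted, and Protocol Section 6.2.1.1 puts new injectable lesions first in the recommended injection order, so they feed the injected-lesion set. Response in injected and uninjected lesions is a secondary endpoint, and SAP Table 9-2 presents the comparison as possible evidence of a systemic effect. Two programmers working from Sections 5 and 6.11 could also reasonably code the same lesion differently.

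**Working it through.** The plan states no figure on this point, so there is none to reproduce. The check compares the texts and then illustrates the effect with assumed measurements.

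**1. Scope of each rule**

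| Rule | Lesions measured | Lesions whose resection triggers the cut-off |
|---|---|---|
| SAP 5, L-ORR | target and new measurable | target |
| SAP 5, maximum decrease, subject level | target and new measurable | target |
| SAP 5, maximum decrease, lesion level | target and new measurable | target |
| SAP 6.11, evaluable lesion sets | target and new measurable | target and new measurable |

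The pathology condition does not differ. Section 5 cuts off when cancer was present or pathology is unknown. Section 6.11 cuts off unless pathology shows no malignant cells, which is the same condition. The two sections disagree only on the kind of lesion.

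**2. Subject level.** Let T be the sum of target diameters at a visit, N the sum of new measurable lesions and B the baseline sum. Maximum decrease is the smallest (T + N)/B, minus 1. Assume B = 100 mm and a non-nodal new lesion seen at visits 2 and 3, then resected with cancer before visit 4 and contributing 0 mm afterwards. With a 30 mm new lesion:

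| Visit | T (mm) | N (mm) | (T + N)/B − 1 |
|---|---|---|---|
| 1 | 90 | 0 | −10% |
| 2 | 75 | 30 | +5% |
| 3 | 65 | 30 | −5% |
| 4, after resection | 65 | 0 | −35% |
| 5 | 65 | 0 | −35% |

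As written, visits 4 and 5 count and the bar is 65/100 − 1 = −35%, whatever the size of the new lesion. With a cut-off at the resection, only visits 1 to 3 count:

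- 10 mm lesion: smallest of 90, 85, 75 gives −25%
- 20 mm lesion: smallest of 90, 95, 85 gives −15%
- 30 mm lesion: smallest of 90, 105, 95 gives −10%
- 40 mm lesion: smallest of 90, 115, 105 gives −10%

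The effect can cross the 30% line. With targets down from 100 to 68 mm and a 25 mm new lesion, the change is (68 + 25)/100 − 1 = −7%. After resection it is 68/100 − 1 = −32%.

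**3. Bound.** New lesions are not in B and N cannot be negative, so (T + N)/B is never below T/B. Surgery on a new lesion can take the bar only as far as the target-only change, which is −35% in the five-visit example.

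**4. Lesion level.** A non-nodal new lesion first measured at 30 mm and recorded as 0 mm after resection shows 0/30 − 1 = −100%. Two such assessments at least 28 days apart would meet L-CR under the Section 5 wording. If the lesion would not otherwise have responded, it adds 1/n to L-ORR: 10 points for n = 10, 5 for n = 20, 2.5 for n = 40. Two such lesions among 40 add 2/40 = 5 points.

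**5. Does Section 6.11 settle it?** Not fully. It defines who enters the evaluable sets, namely lesions with a post-baseline measurement before censoring. A new lesion measured again before surgery stays in the set. Section 6.11 does not say that it replaces the Section 5 cut-off for later values.

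**6. Nodes.** For a resected node not previously present, with cancer or unknown pathology, Appendix D Table 21 records the actual size if the short axis is at least 15 mm, and its footnote carries the initial dimension forward. Such a node does not fall below the 10 mm required for L-CR.

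**The case against.** The strongest reply is that Section 6.11 already names resection as a censoring event for new measurable lesions, so the intention is clear and only wording is at fault. At lesion level much of this stands: a reader might infer that the SAP settles that a resected new lesion counts as L-CR, and it does not. The two sections conflict, and Section 6.11 leans the other way. The reply does not reach the subject-level waterfall, because Section 6.11 concerns lesion sets only.

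Second, the 0 mm entry for a completely resected lesion is written in Appendix D for target lesions, and new nodes follow the carry-forward rule. This also stands. The false L-CR is a risk for non-nodal new lesions and depends on how they are recorded.

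Third, surgery does not create the shrinkage in the bar. It removes an offsetting lesion, and if the targets had reached their smallest size before the new lesion appeared, nothing changes. That is correct and limits the effect. It does not justify using post-surgical assessments when the plan excludes them after resection of a target lesion.

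Fourth, several things must coincide: a new measurable lesion, cancer or unknown pathology, no earlier or simultaneous resection of a cancer-containing target lesion, no new anticancer therapy, and for L-CR a confirming assessment. The documents give no resection frequency, so how often this would occur is unknown.

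Finally, because the BOR definition in SAP Section 5 has the same target-only wording ("complete or partial removal/reduction of any target lesion which contained cancer on pathology evaluation"), a reader might infer that the primary ORR is exposed. The documents do not support that. Appendix D makes the response unevaluable after resection of any lesion with tumor or unknown pathology, except for progression, and Protocol Section 6.6 keeps surgical responses out of ORR and BOR.

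**Conclusion.** The point holds, with low stakes. The Section 5 cut-offs for L-ORR and for maximum tumor burden decrease are narrower than the lesions they govern.

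- **Subject level:** no other SAP text closes the gap, and Appendix D allows post-resection measurements into tumor burden. The bar can be deepened, by 10 to 25 percentage points in the five-visit illustration, but never beyond the target-only change.
- **Lesion level:** Sections 5 and 6.11 conflict. A false L-CR is possible for a non-nodal new lesion if it is recorded as 0 mm; new nodes are largely protected.

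The sizes rest on invented measurements and on 0 mm being used for a resected new lesion. They show direction and scale, not an expected bias. Protocol Section 10.4 confines formal analysis to the Part 2 primary endpoints, so these outputs are descriptive. The primary ORR, BOR and the two-stage decision are not affected.

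**What to change.** In SAP Section 5, under *Lesion objective response rate (L-ORR)* and in both cut-off paragraphs of *Maximum Tumor Burden Decrease*, change *any target lesion* to *any target or new measurable lesion*. Keep the existing pathology condition, which then agrees with Section 6.11.

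For the lesion-level endpoints, add that only the resected lesion is censored. Without that sentence, the wider wording could be read as censoring a subject's other lesions as well.

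The BOR definition needs no change; aligning its wording is optional.

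The cost is a wording change in two definitions and the matching programming specification, with no new data. It is best made before the database lock for the analysis.
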